11.4.4 Other safety variables

11.4.4.1 Physical examination

Subjects with abnormalities in the physical examination will be listed including details of the abnormality.

11.4.4.2 Chest x-ray and TB questionnaire

The results of the chest x-ray and the TB questionnaire will be listed for each subject. For the former listing, the date of the procedure will be included together with the evaluation (normal, abnormal not clinically significant or abnormal clinically significant).

11.4.4.3 C-SSRS

The results of the C-SSRS will be listed for each subject and visit.

12 OTHER ANALYSES

A listing of comments will be presented, if applicable.

This document cannot be used to support any marketing authorization application and any extensions or variations thereof.

PUBLIC COPY

14 APPENDICES

14.1 Treatment group assignment for the TFLs

The treatment group labels and tabulation requirements for each data type are displayed in [Table 14–1](#).

Table 14–1: Treatment group assignment for the TFLs

TFL group	BKZ 320mg + PBO	BKZ 320mg	All Subjects
Subject disposition	X	X	X
Protocol deviations	X	X	X
Demographics	X	X	X
Psoriasis history and Baseline characteristics	X	X	X
Medical history	X	X	X
Prior/concomitant medications	X	X	X
AEs	X	X	X
Safety data (including vital signs, ECGs and laboratory tests)	X	X	
Pharmacodynamic data	X	X	
Efficacy data	X	X	
Pharmacokinetic data	X	X	
ADA	X	X	

ADA=anti-bimekizumab antibody; AE=adverse event; BKZ=bimekizumab; ECG=electrocardiogram; PBO=placebo.

14.2 Hospital Anxiety and Depression Scale

The individual items and associated domains are indicated in [Table 14–2](#).

Table 14–2: Hospital Anxiety and Depression Scale

Anxiety (HADS-A)	Depression (HADS-D)
I feel tense or wound up	I still enjoy the things I used to enjoy
I get a sort of frightened feeling as if something awful is about to happen	I can laugh and see the funny side of things
Worrying thoughts go through my mind	I feel cheerful
I can sit at ease and feel relaxed	I feel as if I am slowed down
I get a sort of frightened feeling like butterflies in the stomach	I have lost interest in my appearance
I feel restless as if I have to be on the move	I look forward with enjoyment to things
I get sudden feelings of panic	I can enjoy a good book or radio or television program

The scores for each item range from 0 to 3, with higher scores indicating more severe anxiety or depression. The total score for each domain ranges from 0 to 21. A score of <8 for a given domain is considered as normal.

In case of missing data, the following rules will be applied:

- If a maximum of 1 item is missing in a given domain, the missing item will be imputed with the mean score from the remaining completed items within the same domain
- If more than 1 item is missing in a given domain, the domain subscore will not be calculated

14.3 Flow cytometry variables

The individual variables to be reported are presented in [Table 14–3](#).

Table 14–3: Flow cytometry variables

Cell Subset/Population	Phenotype	Reportable Units
TBNK Panel		
Lymphocytes	CD45+	% of singlets
Total T Cells	CD3+	% of Lymphocytes
T helper Cells	CD3+ CD4+	% of Lymphocytes
Cytotoxic T cells	CD3+ CD4+	% of Lymphocytes
B lymphocytes	CD3- CD19+	% of Lymphocytes
DC, Monocytes and NK cells	CD3- CD19-	% of Lymphocytes
NK cells	CD3- CD16+ CD56+	% of Lymphocytes
Activated T cells	CD69+	% of T cells
Activated Th	CD69+	% of T helper cells
Activated Tc	CD69+	% of Cytotoxic T cells
Activated B cells	CD69+	% of B cells
Activated NK cells	CD69+	% of NK cells
Th Subset Panel		
Lymphocytes	CD45+	% of singlets
Total T Cells	CD3+	% of Lymphocytes
T helper Cells	CD3+ CD4+	% of Lymphocytes
Th1	CXCR3+	% of T helper Cells
Th2	CCR6-CCR4+	% of T helper Cells
Th17/22	CCR6+ CCR4+	% of T helper Cells
Th17	CCR6+CCR4+CCR10-	% of T helper Cells
Th22	CCR6+CCR4+CCR10+	% of T helper Cells
Activated Th1	CD69+	% of Th1
Activated Th2	CD69+	% of Th2
Activated Th17	CD69+	% of Th17

CCR=chemokine receptor; CD=cluster of differentiation; CXCR=CXC chemokine receptor; DC=dendritic cell; NK=natural killer; TBNK=T cell, B cell and NK cell assay ;Tc=T cytotoxic ;Th=T helper.

14.4 Classification of markedly abnormal laboratory values based on CTCAE grades

The criteria for assessing laboratory values as markedly abnormal are presented in [Table 14–4](#).

Table 14–4: Criteria for markedly abnormal laboratory tests

Category	Panel	Variable	Criteria (CTCAE Grade 3 and above)	
Hematology	Red blood cell	Hemoglobin (Decrease)	<80 g/L	
		Hemoglobin (Increase)	>4 g/dL (>40 g/L) above ULN OR >4 g/dL (>40 g/L) above baseline if baseline is >ULN	
	White blood cell	WBC count (Decrease)	<2.0 x 10 ⁹ /L	
		WBC count (Increase)	>100 x 10 ⁹ /L	
	White blood cell differential	ALC (Decrease)	<0.5 x 10 ⁹ /L	
		ALC (Increase)	>20 x 10 ⁹ /L	
		ANC	<1.0 x 10 ⁹ /L	
	Platelet	Platelet	<50 x 10 ⁹ /L	
	Chemistry	Liver function	ALT	>5.0 x ULN
			ALP	>5.0 x ULN
AST			>5.0 x ULN	
Total bilirubin			>3.0 x ULN	
GGT			>5.0 x ULN	
Kidney function		Creatinine	>3.0 x baseline value	
			OR >3.0 x ULN	
		Electrolytes	Calcium (Decrease)	<1.75 mmol/L
			Calcium (Increase)	>3.1 mmol/L
			Magnesium (Decrease)	<0.4 mmol/L
			Magnesium (Increase)	>1.23 mmol/L
			Potassium (Decrease)	<3.0 mmol/L
			Potassium (Increase)	>6.0 mmol/L
Sodium (Decrease)	<130 mmol/L			
	Sodium (Increase)	>155 mmol/L		

Category	Panel	Variable	Criteria (CTCAE Grade 3 and above)
	Lipids	Total cholesterol	>10.34 mmol/L

ULN=upper limit of normal.

14.5 Treatment-emergent abnormal liver values

The criteria for identifying treatment-emergent liver function abnormalities are presented in [Table 14–5](#). Subjects will be counted in all applicable categories for the tabulations ie, a subject with ≥ 5 x ULN in AST will also be counted in the ≥ 3 x ULN in AST category, the ≥ 3 x ULN in AST or ALT category and the ≥ 5 x ULN in AST or ALT category.

Table 14–5: Definition of treatment-emergent liver function values

Criterion
≥ 3 x ULN increase for AST
≥ 5 x ULN increase for AST
≥ 10 x ULN increase for AST
≥ 20 x ULN increase for AST
≥ 3 x ULN increase for ALT
≥ 5 x ULN increase for ALT
≥ 10 x ULN increase for ALT
≥ 20 x ULN increase for ALT
≥ 3 x ULN increase for AST or ALT
≥ 5 x ULN increase for AST or ALT
≥ 10 x ULN increase for AST or ALT
≥ 20 x ULN increase for AST or ALT
≥ 1 x ULN increase for bilirubin
≥ 1.5 x ULN increase for bilirubin
≥ 1.5 x ULN increase for ALP
≥ 1 x ULN increase for bilirubin and 3 x ULN increase of either AST or ALT (at the same visit)
≥ 2 x ULN increase for bilirubin and 3 x ULN increase of either AST or ALT (at the same visit)

ALP=alkaline phosphatase; ALT=alanine aminotransferase; AST=aspartate aminotransferase; ULN=upper limit of normal.

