19. Subject has a history of uncompensated heart failure, fluid overload, or myocardial infarction, or evidence of new onset ischemic heart disease or in the opinion of the Investigator other serious cardiac disease, within 12 weeks prior to Baseline.
- 20a. Subject has >2x upper limit of normal (ULN) of any of the following: alanine aminotransferase (ALT), aspartate aminotransferase (AST), alkaline phosphatase (ALP), or >ULN total bilirubin ( $\geq 1.5 \times \text{ULN}$  total bilirubin if known Gilbert's syndrome). If subject has elevations only in total bilirubin that are >ULN and <1.5xULN, fractionate bilirubin to identify possible undiagnosed Gilbert's syndrome (ie, direct bilirubin <35%).

Tests that result in ALT, AST, or ALP up to 25% above the exclusion limit may be repeated once for confirmation during the Screening Period. Upon retesting, subjects whose ALT, AST, or ALP remain above the thresholds defined above, should not be randomized.

For randomized subjects with a baseline result >ULN for ALT, AST, ALP, or total bilirubin, a baseline diagnosis and/or the cause of any clinically meaningful elevation must be understood and recorded in the Case Report form (CRF).

If subject has >ULN ALT, AST, or ALP that does not meet the exclusion limit at screening, repeat the tests, if possible, prior to dosing to ensure there is no further ongoing clinically relevant increase. In case of a clinically relevant increase, inclusion of the subject must be discussed with the Medical Monitor.
21. Subjects with clinically significant laboratory abnormalities (eg, creatinine >1.5xULN, neutropenia <1.5x10^9/L, hemoglobin <8.5g/dL, lymphocytes <1.0 x10^9/L, platelets <100 x10^9/L). Individual screening tests for which the results are in error, borderline, or indeterminate for inclusion in the study, can be repeated once for confirmation during the screening period if they are within 25% of the exclusion limit. Upon retesting, subjects whose results remain outside this threshold should not be randomized.
22. Subjects with any other condition which, in the Investigator's judgment, would make the subject unsuitable for inclusion in the study.
23. Subjects have been exposed to more than 1 biological response modifier (limited to anti-TNF or IL-12/-23) or have received any biologic response modifier during the three months prior to the Baseline Visit. The list of prohibited medications is presented in [Section 7.8.2](#).

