11.3 Clinical laboratory evaluations

Laboratory data (clinical chemistry, hematology, and urinalysis) and changes from Baseline (if applicable) for numeric variables will be listed by treatment group and visit. Any laboratory variables with values that are BLQ or ALQ will be handled as described in [Section 4.2.2](#) for calculation of changes from Baseline and for summary tables. Values outside the reference range for the numeric variables will be flagged in the listings and in addition, will be listed separately. The reference ranges will also be reported in the listings.

Clinical chemistry and hematology variables will be summarized by treatment group (including All Subjects) at each visit, for both absolute values and changes from Baseline.

Laboratory variables will be grouped according to the laboratory function panel and categorized as normal, high or low, if applicable, based on the reference range supplied by the analytical laboratory. For selected variables that are identified in [Table 11-1](#), the change in category from Baseline will be presented in shift tables at all post-Baseline visits.

The number and percentage of subjects with treatment-emergent markedly abnormal (TEMA) laboratory results (to match the TEAE definition stated in [Section 11.1.3](#)) will be tabulated by treatment group and visit. Markedly abnormal laboratory values will be defined as those categorized as Grade 3 and above based on the ranges defined as per the Common Terminology Criteria for Adverse Events (CTCAE) Version 4.03 (2016). These are provided in [Table 14-4](#). The tabulation will include a category for the incidence of TEMA results over all visits which will also count unscheduled measurements.

In addition, for absolute neutrophil count (ANC), all grade 2 CTCAE abnormalities ($<1.5 - 1.0 \times 10^9/L$) will be listed separately, with results from all visits for any subject that has any grade 2 abnormality.

Laboratory measurements meeting the criteria for TEMA will be listed separately for hematology and chemistry. The listings will include all measurements for any variable with at least one TEMA result for each subject.

Any additional laboratory variables not included in the outputs described previously will be listed separately. These will include the following:

- Serology
- Pregnancy tests (serum and urine)
- Follicle stimulating hormone (FSH) (only for postmenopausal women)

The results of the Quantiferon TB Gold test will be listed separately.

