Subjects with treatment-emergent liver function test abnormalities at any post-Baseline visit will be summarized (number and percentage of subjects) by treatment group. The criteria for this tabulation are presented in [Section 14.5](#).

Table 11–1: Clinical laboratory measurements

Category	Panel	Variable
Serology	Serology	HIV1-Ab, HIV2-Ab, HBsAg, anti-HBc, anti-HBs, anti-HCV-Ab, TB
Hematology	Red blood cell	RBC count ^a , hemoglobin, hematocrit
	Red blood cell indices	MCH, MCHC, MCV
	Platelet	Platelets
	White blood cell	WBC count ^a
	White blood cell differential	Absolute counts: ANC ^a , basophils, eosinophils, ALC, monocytes, atypical lymphocytes (if indicated) Percentages: neutrophils/leukocytes, basophils/leukocytes, eosinophils/leukocytes, lymphocytes/leukocytes, monocytes/leukocytes.
Chemistry	Electrolytes	Sodium, chloride, potassium, calcium, magnesium
	Kidney function	BUN, creatinine
	Liver function	AST ^a , ALT ^a , GGT ^a , ALP ^a , LDH ^a , total bilirubin (direct bilirubin, indirect bilirubin, if indicated)
	Lipids	Total cholesterol ^a
	Metabolic function	Glucose
	Hormones	FSH ^b
	Fertility	Pregnancy test ^c
	Other	CRP
Urinalysis	Dipstick	pH, protein, blood, leukocyte esterase, nitrite, glucose

Table 11–1: Clinical laboratory measurements

Category	Panel	Variable
	Urine sediment (if indicated)	WBC, RBC, epithelial cells (squamous, transitional and renal tubular), hyaline casts, WBC casts, RBC casts, waxy casts, granular casts, calcium oxalate crystals, uric acid crystals, triphosphate crystals, yeast, bacteria, amorphous urates, amorphous phosphates

ALC=absolute lymphocyte count; ALP=alkaline phosphatase; ALT=alanine aminotransferase; ANC=absolute neutrophil count; AST=aspartate aminotransferase; BUN=blood urea nitrogen; CRP=C-reactive protein; FSH=follicle stimulating hormone; GGT=gamma glutamyltransferase; anti-HBc= hepatitis B core antibody; anti-HBs=hepatitis B surface antibody; HbsAg=hepatitis B surface antigen; HCV-Ab=hepatitis C virus antibody; HIV1-Ab=human immunodeficiency virus 1 antibody; HIV2-Ab= human immunodeficiency virus 1 antibody; LDH=lactate dehydrogenase; MCH=mean cell hemoglobin; MCHC=mean cell hemoglobin concentration; MCV=mean cell volume; RBC=red blood cell; TB=tuberculosis; WBC=white blood cell.

^a Shift tables will be presented for these variables.

^b FSH performed on postmenopausal females who have been postmenopausal for ≥ 1 year and last menstrual cycle occurred < 2 years ago.

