14.7 Treatment-emergent markedly abnormal vital signs values

The criteria for identifying TEMA/PCS vital signs values are provided in [Table 14-6](#).

Table 14-6: TEMA/PCS criteria for vital signs

Variable	Unit	Low ^a	High ^a
Systolic blood pressure	mmHg	Value ≤ 90 and ≥ 20 decrease from Baseline	Value ≥ 180 and ≥ 20 increase from Baseline
Diastolic blood pressure	mmHg	Value ≤ 50 and ≥ 15 decrease from Baseline	Value ≥ 105 and ≥ 15 increase from Baseline

Note: the change in measurement (increase or decrease) will be calculated relative to the value obtained at Baseline.

^a Both conditions must be satisfied for a measurement to be considered TEMA/PCS.

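### SAP Table 14-5 labels liver values treatment-emergent without a Baseline comparison, so its bilirubin ≥1 x ULN and ALP ≥1.5 x ULN rows can count stable values that eligibility allows

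*SAP*

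**What the plan says.** **Liver table.** SAP Section 11.3 states: "Subjects with treatment-emergent liver function test abnormalities at any post-Baseline visit will be summarized". The criteria are in Table 14-5, whose 17 rows are multiples of ULN followed by the word *increase*, such as "≥ 1 x ULN increase for bilirubin" and "≥ 1.5 x ULN increase for ALP". No row names Baseline. The introduction to the table explains that "a subject with ≥ 5 x ULN in AST will also be counted in the" lower AST category and the matching AST-or-ALT categories.

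**Grade 3 table.** Section 11.3 also tabulates "treatment-emergent markedly abnormal (TEMA) laboratory results (to match the TEAE definition stated in" Section 11.1.3). It adds: "Markedly abnormal laboratory values will be defined as those categorized as Grade 3 and above based on the ranges defined" in CTCAE, as listed in Table 14-4. Section 11.1.3 is about time at risk. The TEAE definition is in Section 11.2.1 and is a rule about the start date of an adverse event.

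**Entry limits.** Protocol criterion 20a (Section 6.2) excludes ALT, AST or ALP above 2 x ULN and total bilirubin above ULN, with a limit of 1.5 x ULN or more for known Gilbert's syndrome. It foresees subjects in between: "If subject has elevations only in total bilirubin that are >ULN and <1.5xULN, fractionate bilirubin". It also asks for the cause of clinically meaningful elevations in randomized subjects whose Baseline liver values exceed ULN.

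**Vital signs, for comparison.** Table 14-6 pairs a level with a change from Baseline, and its footnote reads: "Both conditions must be satisfied for a measurement to be considered TEMA/PCS".

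**The concern.** A table headed treatment-emergent should separate what appeared after dosing from what was there before. Table 14-5 asks only whether a value measured after Baseline reaches a threshold. If entry limits let a subject start at or above that threshold, an unchanged value is reported as having emerged on bimekizumab.

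This matters because liver enzyme and bilirubin changes are adverse events for special monitoring (protocol Section 12.1.3). The planned arms are small and unequal, 30 and 15. Both arms receive bimekizumab at Baseline and Week 4, so no concurrent placebo rate shows how often such values occur without the drug.

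**Working it through.** The plan gives no figure to reproduce. The check compares the most extreme value that eligibility allows with each threshold.

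**1. Level or rise?** The AST example treats a multiple of ULN as a level reached. A literal rise from Baseline gives different counts: ALT going from 2 to 4.5 x ULN reaches the ≥3 x ULN level, but the rise is 4.5 − 2 = 2.5 x ULN and fails. The term therefore needs a definition under either reading. The steps below use the level reading.

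**2. Table 14-5 (17 rows) against criterion 20a.**

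| Rows | Highest eligible stable value | Threshold | Reachable? |
|---|---|---|---|
| 12 AST and/or ALT rows | 2 x ULN | 3 x ULN or more | No |
| Bilirubin ≥1 x ULN | <1.5 x ULN (known Gilbert's); exactly ULN otherwise | 1 x ULN | Yes |
| Bilirubin ≥1.5 x ULN | <1.5 x ULN | 1.5 x ULN | No |
| ALP ≥1.5 x ULN | 2 x ULN | 1.5 x ULN | Yes |
| 2 combined rows | AST/ALT 2 x ULN | AST/ALT 3 x ULN | No |

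Two of 17 rows are open. Examples are Gilbert's syndrome with bilirubin steady at 1.2 x ULN, and ALP steady at 1.7 x ULN.

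**3. Table 14-4 (23 rows) against criteria 20a and 21.**
- Ten rows are closed by numeric limits: ALT, AST and ALP (2 against >5 x ULN); bilirubin (<1.5 against >3 x ULN); creatinine (1.5 against >3 x ULN); hemoglobin decrease (85 against <80 g/L); ANC (1.5 against <1.0); ALC decrease (1.0 against <0.5); platelets (100 against <50); and, by implication, WBC decrease (ANC + ALC ≥ 1.5 + 1.0 = 2.5 against <2.0).
- Hemoglobin increase has its own Baseline term. So does creatinine, already listed as closed.
- Twelve rows have no numeric entry limit: GGT, total cholesterol, WBC increase, ALC increase and eight electrolyte rows.
- Count: 10 + 1 + 12 = 23.

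**4. Size per subject.** Arm A: 1/30 = 3.3 percentage points. Arm B: 1/15 = 6.7 percentage points.

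**5. How many subjects?** The documents give no prevalence. As an assumption only, let a share p of the 45 subjects have a stable value in an exposed row. The expected number is 45p, and the chance of at least one is 1 − (1 − p)^45.

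| Assumed p | Expected | Chance of at least one |
|---|---|---|
| 2% | 0.9 | 0.60 |
| 5% | 2.25 | 0.90 |
| 10% | 4.5 | 0.99 |

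**The case against.** The best defence has four parts.

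- **The word *increase* already implies Baseline.** It might, but the SAP's example points to a level and no definition is given. This shows ambiguity; it does not settle the reading.
- **Grade 3 results must match the TEAE definition, which treats earlier starts as pre-treatment.** That could be read as excluding an abnormality present before dosing. It remains a date rule for events, does not say how to treat a laboratory value that was already abnormal, and points to the wrong section. Section 11.3 does not repeat the clause for the liver table.
- **Baseline context is planned elsewhere.** There are change-from-Baseline summaries, shift tables for ALP, GGT and total cholesterol, and listings of all measurements for any variable with a Grade 3 result. A reader could therefore trace many cases. However, total bilirubin has no shift table, and the ALP shift uses only low, normal and high, so it cannot show whether 1.5 x ULN was already exceeded.
- **A stable Grade 3 value is improbable.** Criterion 21 excludes clinically significant abnormalities through an open list, and withdrawal criterion 11 deals individually with Grade 3 laboratory values. This stands, and is why the Grade 3 part is only a remote concern.

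A reader might infer that none of the treatment-emergent laboratory tables has a Baseline condition, or that the transaminase rows and the combined rows are contaminated. The documents do not support this: two rows of Table 14-4 refer to Baseline, and the 2 x ULN entry limit keeps stable eligible values out of every row that needs AST or ALT. Stable Gilbert's bilirubin could supply half of the first combined row, but that row would still need AST or ALT to rise to 3 x ULN.

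**Conclusion.** The concern holds for two rows of Table 14-5, bilirubin ≥1 x ULN and ALP ≥1.5 x ULN. On the level reading, a stable value that criterion 20a admits is counted there as treatment-emergent. For Table 14-4 it holds only as an unclear rule with a wrong cross-reference, relevant mainly to GGT, total cholesterol and electrolytes.

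Each miscounted subject would add 3.3 points in arm A or 6.7 in arm B, once per row, because the liver table is not split by visit. It would be tempting to conclude that a false liver signal is to be expected. The documents give no basis for a number of affected subjects, and the study is exploratory and not powered for conclusive safety analysis.

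The conclusion assumes the level reading, the planned arm sizes, and laboratory values at first dose that still satisfy the entry limits. That last assumption can fail, since protocol Section 6.1 requires only the pregnancy result from the Baseline Visit to be known before dosing.

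**What to change.** In SAP Sections 11.3, 14.4 and 14.5:

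1. Define *increase* as a level reached.
2. Count a result as treatment-emergent only if the criterion is met after the first dose and was not met at the Table 3-1 Baseline.
3. Report subjects who met it at Baseline in a separate row for abnormalities present at Baseline, split into those who did and did not worsen by a pre-specified amount relative to Baseline. The sponsor should set that amount before unblinding. Protocol Table 12-3 already pairs a multiple of ULN with a multiple of baseline, so the form is familiar.
4. Point the TEAE reference in Section 11.3 to Section 11.2.1. Section 11.4.1 repeats the same wrong reference.

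The split in step 3 is needed. Counting only a move to a higher listed category would hide real worsening, because ALP has a single row in Table 14-5 and each Table 14-4 criterion is a single Grade 3-and-above category. ALP going from 1.6 to 4.9 x ULN would never appear.

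The cost is SAP wording, one programming condition and the extra rows. No new data are needed.

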14.6 Adverse events of special monitoring

The following AESM are defined for bimekizumab and will be summarized separately as described in [Section 11.2](#):

- Major cardiovascular events
- Serious infections, including opportunistic infections and TB

- Malignancies including lymphoma
- Cytopenias
- Neuropsychiatric events (in particular, depression and suicide)
- Inflammatory bowel disease
- Anaphylactic reaction (hypersensitivity and anaphylactic reactions)
- Hepatic events and drug-induced liver injury

All AESM tabulations will be presented by treatment group, SOC, HLT and PT, based on the SS, and will include the EAIR and EAER.

